VERSION DATE APRIL 22, 2016

TITLE: A comparison of early deployment of a video capsule (Endocapsule EC-10: Olympus Tokyo. Japan) in the Emergency Department versus conventional work-up of non-hematemesis gastrointestinal bleeding [NHGIB].

NCT02442830

[name], PHD, PRINCIPAL INVESTIGATOR

INVESTIGATOR STUDY PLAN - REQUIRED

1) Title

A comparison of early deployment of a video capsule (Endocapsule EC-10: Olympus Tokyo. Japan) in the Emergency Department versus conventional work-up of non-hematemesis gastrointestinal bleeding [NHGIB].

2) IRB Review History*

Not applicable.

3) Objectives*

The objectives of this study are to test whether there are statistically significant differences between the conventional workup of NHGIB by endoscopy [upper, lower and other tests], compared with deployment of a video capsule VCE as the first test followed by the most appropriate endoscopic procedure based on VCE findings, if needed. We propose to examine differences in time to diagnosis, reduction in numbers of procedures, and length of stay between a conventional workup protocol and our proposed protocol of early capsule endoscopy deployment.

4) Background*

After 40 years of considering gastrointestinal bleeding as upper or lower and largely ignoring the small intestine, there is accumulating evidence that the conventional approach to the assessment of NHGIB could be improved by early deployment of a video capsule as the first diagnostic test. Currently, video capsule endoscopy is considered the gold standard as the diagnostic test for small intestinal bleeding. In a recent study at UMass of 336 patients who presented to the ED with complaints of gastrointestinal bleeding 36 patients (10.7%) were given a video capsule during their stay.¹

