The use of capsule endoscopy has been approved by the FDA since 2001 for small intestinal bleeding obscure GI Bleeding]. It is very safe, no deaths associated with its use have been reported. More than two million capsule have been used and obstruction and perforation are extremely rare.

Interest in the broader use of VCE is accumulation. In 2004 Sachdev et al reported a pilot study on the use of early use of VCE in acute NHGIB. This showed a 50% reduction to time to diagnosis in 24 patients. More recently studies of VCE deployed in the ED, in patients with upper GI bleeding showed improved management. Our group recently demonstrated that the closer a video capsule is performed to the time of bleeding the higher the likelihood of locating the sources and the higher the therapeutic intervention rate.³ We also have demonstrated that the use of capsule endoscopy in patients with NHGIB has a higher diagnostic yield than does colonoscopy. With improved diagnostic yields, capsule endoscopy may help clinicians by providing guidance in the management of patients with NHGIB.

This protocol is be the first attempt to prospectively examine this concept in a large randomized prospective trial. The questions are, can early capsule intervention decrease time to diagnosis, numbers of procedures and hospital length of stay in patients with non-hematemesis gastrointestinal bleeding.

References:

1. Jawaid S GB, Singh, A, Marshall C, and Cave D. . The epidemiology of gastrointestinal bleeding in an academic emergency department as a basis for

INVESTIGATOR STUDY PLAN - REQUIRED

reconfiguring the conventional approach to its diagnosis and management. .
Gastrointestinal Endoscopy 2013;77:Supplement, Page AB483.

5) Inclusion and Exclusion Criteria*

Inclusion Criteria:

- Age greater than 18 years old
- New onset of melena or hematochezia
- Able to sign consent
- Hemodynamically stable (i.e. blood pressure >100/60 or pulse <110 at the time of consent)

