- ED must plan to admit patient to the hospital or Clinical Decision Unit.

Exclusion criteria:

- Adults unable to consent
- Individuals who are not yet adults (infants, children, teenagers)
- Pregnant women
- Prisoners
- Prior history of gastroparesis
- Prior history of gastric, or small bowel surgery
- Prior history of inflammatory bowel disease
- Concern for infectious colitis
- Non-English speaking
- Evidence of dysphagia at the time of presentation
- Presence of bright red blood per rectum
- Allergy to metoclopramide or erythromycin
- Code status of DNR/DNI or CMO
- Prior history of abdominal radiation
- Presence of ICD or pacemaker or other implanted electronic devices
- Abdominal pain suggesting an acute abdomen or obstruction. In clinical practice, only patients with crampy abdominal pain due to

INVESTIGATOR STUDY PLAN - REQUIRED

Crohn's disease, previous intestinal surgery and a previous history of radiation therapy require a patency capsule or CT enterography before capsule endoscopy.

- Patients who cannot undergo surgery

6) Study-Wide Number of Subjects*

Not applicable – not a multi-site study

7) Study-Wide Recruitment Methods*

Not applicable – not a multi-site study

8) Study Timelines*

1. The participation of individual subjects in this study will be approximately 31-40 days (the length of their hospitalization plus an additional thirty days for follow up).
2. The duration anticipated to enroll all study subjects is about 24 months.
3. The estimated date for the investigators to complete this study and data analysis is two years.

9) Study Endpoints*

The primary endpoint will be time to diagnosis. Secondary endpoints will include hospital length of stay, number of invasive procedures, blood product transfusions.

10) Procedures Involved*

Screening

Patients presenting to the Emergency Room with NHGIB (defined as melena or hematochezia) will be identified by a member of the ED staff.

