Depending on the findings a recommendation will be made as to the next most appropriate test. See attached Figure 1. If blood is found in the esophagus, stomach or duodenum an upper endoscopy is recommended. If blood is seen in the small intestine, it will be recommended that the subject next have a push enteroscopy, deep enteroscopy, or angiography. If blood in right colon, colonoscopy may be performed or deferred to colonoscopy as an outpatient, if active bleeding has ceased. If the capsule study is not diagnostic and no blood is seen in the GI tract and there is no ongoing hematochezia, the subject will be placed in ED observation for up to 23 hours and evaluated for potential discharge and follow-up by gastroenterology as an outpatient.

INVESTIGATOR STUDY PLAN - REQUIRED

If no bleeding/ blood or a likely source is found. These individuals will be considered for observation, early discharge and follow up in the GI outpatient setting.

For most subjects, the capsule will pass in a bowel movement within 24 - 72 hours of ingestion.

An equal number subjects [up to 80] will be randomized to the “conventional workup group”. “Conventional Workup” for NHGIB could include upper endoscopy, colonoscopy, and additional capsule or small bowel enteroscopy depending on the subject’s presentation and the results of the workup performed by the gastroenterology team. For some subjects, the VCE would be done as part of standard of care estimated that 5-15% of patients will have small intestinal bleeding. For patients requiring a video capsule endoscopy as part of “conventional workup” the patients will be given the same Olympus video capsule that is used in the “Early Capsule” group. Further management would be as standard of care. These subjects will be discharged on the recommendation of the attending hospitalist after completion of treatment.

Review and Follow-Up

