During hospitalization, data will be recorded from ED pulse check, Meditech, Soarian, and Allscripts regarding fluid administration, transfusion of pRBC, initial hematocrit, times and types of procedures (e.g. upper endoscopy, enteroscopy, colonoscopy), time from entry to ED to time to diagnosis (i.e. localization of source of bleeding), admission disposition (i.e. clinical decision unit, regular floor, ICU), time of discharge. The procedures involved in the hospitalization (i.e. upper endoscopy, enteroscopy, and colonoscopy) will be done as part of standard of care. All of this information will be linked to the subject’s study ID number as described above. This data collection is for research purposes only.

In addition, the costs of the procedures will be collected through financial services. The costs that will be collected are both the fixed and variable costs associated with each patient in the study. We will also collect the direct and indirect costs allocated to each patient. All charges associated with the admission for each patient in the study will have costs allocated. This will be evaluated as an additional data point to compare the two arms of the study. No additional PHI will be collected.

Telephone Follow-Up

Subjects will also be contacted by phone by a research staff member at two different time points following their discharge from the hospital. These time points will be at 3 days (+2 days) and 30 days (+/- 3 days) following their discharge. At these time points a staff member will call a subject to obtain information about whether or not a patient has had recurrent bleeding and whether or not the patient had to be readmitted to a hospital or emergency room for

INVESTIGATOR STUDY PLAN - REQUIRED

recurrent bleeding. Please see attached form for telephone script that staff member will read along with particular questions that will be asked.

No more than three attempts will be made at each time point to reach the subject. If a message is left, it will be "Hello, this is [name] calling from UMass looking to speak with [subject]. Please call back at [number] at your earliest convenience. Thank you."

11) Data and Specimen Banking*

N/A – no data banking.

12) Data Management*

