PUBLISH DATE JUNE 20, 2018

STATISTICAL ANALYSIS PLAN

TITLE: A comparison of early deployment of a video capsule (Endocapsule EC-10: Olympus Tokyo. Japan) in the Emergency Department versus conventional work-up of non-hematemesis gastrointestinal bleeding [NHGIB].

NCT02442830

[name], PHD, PRINCIPAL INVESTIGATOR

STATISTICAL ANALYSIS PLAN

Study outcomes:

The primary outcome for this study was the rate of localization of bleeding during hospitalization. Localization of bleeding was defined as identification of blood or identification of a lesion with high-risk stigmata of recent hemorrhage (SRH). Secondary outcomes included, overall rate of localization of bleeding by the end of admission, anatomic location of bleeding or the bleeding source, rate of endoscopic therapy, rate of readmission, rate of diagnosis of vascular lesions (defined as Dieulafoy's lesions or angioectasias), rate of re-bleeding within 30 days of discharge, rate of all-cause mortality within 30 days of hospitalization, cumulative direct hospital costs by the end of admission, and overall rate of identifying the etiologic diagnosis.

Sample size calculation:

The study was planned as a superiority trial and the estimated probability of localization of bleeding during hospitalization in the Early Capsule arm to be two times greater than that of the Standard of Care arm (i.e. estimated hazard ratio of 2.00). We found no prior studies similar to our methodology, so prior experience at our institution guided the estimation of effect. Power analysis revealed that for this effect size to be detected (80% chance) as significant at the 5% level, a sample of at least 72 patients (36 per group) would be required.

Statistical analysis:

Patient characteristics were described as means with standard deviation (SD) or as proportions. Time to localization and time to first procedure were described using medians with interquartile range (IQR). Hospital costs were described in US dollars (USD).

Independent variables selected for analysis included those previously suggested as prognostic indices for NHGIB. Variables chosen for analysis included gender, race, age, vital signs at admission, use of anticoagulants, use of non-steroidal anti-inflammatory drugs (e.g. aspirin and ibuprofen; NSAIDs), use of a P2Y₁₂ inhibitor (e.g. clopidogrel), factors that contribute to the Glasgow-Blatchford Score, and type of bleeding at admission (i.e. hematochezia, melena, or symptomatic anemia).

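### Procedures (as collected) and direct cost (as defined) stop at discharge, which the early-capsule pathway can bring forward, so postponed work could be counted as work avoided

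*Protocol*

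**What the plan says.** **Objective and endpoints.** Protocol section 3 states: "We propose to examine differences in time to diagnosis, reduction in numbers of procedures, and length of stay". Section 4 asks "can early capsule intervention decrease time to diagnosis, numbers of procedures and hospital length of stay", and section 15 gives fewer procedures in the early group as part of the hypothesis. Section 9 reads: "Secondary endpoints will include hospital length of stay, number of invasive procedures, blood product transfusions". It sets no time window for the procedure count. The SAP's list of outcomes does not include number of procedures. It does include rate of endoscopic therapy, again without a window, and "cumulative direct hospital costs by the end of admission".

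**Data collection.** Protocol section 10, Review and Follow-Up, opens with "During hospitalization, data will be recorded from ED pulse check, Meditech, Soarian, and Allscripts" and lists procedure times and types among the items. Costs in the same section are those allocated to the admission. Under Telephone Follow-Up, the calls at 3 and 30 days after discharge are to establish "whether or not a patient has had recurrent bleeding and whether or not the patient had to be readmitted", or returned to an emergency room, for bleeding. The script is an attachment that is not in the public file.

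**Pathways.** In the early-capsule arm, section 10 says: "If blood in right colon, colonoscopy may be performed or deferred to colonoscopy as an outpatient, if active bleeding has ceased". If the capsule shows no blood and there is no ongoing hematochezia, "the subject will be placed in ED observation for up to 23 hours and evaluated for potential discharge", with outpatient gastroenterology follow-up. Conventional-arm patients leave when the attending hospitalist recommends it, once treatment is finished. Their care is otherwise standard.

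**The concern.** A colonoscopy done on the ward is in the data. The same colonoscopy done after discharge is not, so far as the documents describe. Only the early-capsule arm has a written route from the first to the second. The end of the counting window is thus a consequence of the assigned strategy, and the two arms may be observed for different lengths of time for that reason.

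Randomization does not remove this, because the difference arises after randomization. The covariate adjustment in the SAP cannot remove it either, because it works on characteristics at admission. At stake is whether a lower procedure count or a lower cost means that early capsule spared patients and the hospital some work, or only moved part of it past the last day on which anyone counted.

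**Working it through.** **Is there a figure in the plan to reproduce?** No. The documents give no expected procedure count, no cost difference and no deferral share. The planned group sizes (80 per arm in Protocol sections 12 and 25; 36 per group in the SAP) serve below only as denominators.

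**Step 1. The window for each outcome.**

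| Outcome | Where listed | Window |
|---|---|---|
| Number of invasive procedures | Protocol section 9; not in the SAP | None stated; data collection is during hospitalization |
| Direct hospital cost | SAP secondary outcome; an extra data point in Protocol section 10 | Explicit: end of admission |
| Rate of endoscopic therapy | SAP secondary outcome | None stated; in-hospital only by inference from the data sources |

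**Step 2. Illustration with any endoscopy deferred.** Hidden procedures = deferral share × patients in the arm, at one procedure per patient. The lower share of 10% is an assumption. The upper share borrows the non-diagnostic fraction in Protocol section 4: (36 − 26)/36 = 10/36 = 27.8%.
- 80 per arm: 0.10 × 80 = 8, and 0.278 × 80 = 22.
- 36 per arm: 0.10 × 36 = 3.6, and 0.278 × 36 = 10.

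**Step 3. Illustration with colonoscopy only.** Section 4 reports 152 upper endoscopies and 64 colonoscopies. Colonoscopy is 64/(152 + 64) = 64/216 = 29.6% of the two. If true use is equal in both arms and a share f of early-arm colonoscopies is deferred, the counted total falls by f × 29.6%: 3.0% at f = 10%, 7.4% at 25% and 14.8% at 50%.

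**Step 4. Could this produce a significant difference?** Take the proportion of patients with an in-hospital colonoscopy, which is not itself a planned endpoint. Let the true rate be p in both arms and the counted early-arm rate be q = p(1 − f). With n per arm and m the mean of p and q, the chance of a significant two-sided 5% test is approximately

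Φ{[(p − q)√n − 1.96√(2m(1 − m))] / √(p(1 − p) + q(1 − q))}.

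For p = 0.30, f = 25%, n = 80: q = 0.225, m = 0.2625, and (0.671 − 1.220)/0.620 = −0.885, which gives 0.19.

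| True rate p | f | Hidden per 80 | Chance, 80 per arm | Chance, 36 per arm |
|---|---|---|---|---|
| 19% (64/336) | 25% | 3.8 | 12% | 8% |
| 30% (assumed) | 25% | 6.0 | 19% | 11% |
| 50% (assumed) | 25% | 10.0 | 36% | 19% |
| 19% | 50% | 7.6 | 40% | 21% |
| 30% | 50% | 12.0 | 62% | 33% |
| 50% | 50% | 20.0 | 91% | 59% |

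At f = 10% the chances are 5% to 9% at 80 per arm and 4% to 6% at 36 per arm, so a small deferral share matters little. All of this assumes no deferral in the conventional arm.

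**The case against.** The other side has several good points.

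- **Only cost has a stated cut-off.** For procedures it follows from how the data are collected, and for endoscopic therapy it is only inferred. Section 12 speaks of medical record review without a discharge limit. This stands: for those two outcomes the window first needs to be stated.
- **The asymmetry is not certain.** Deferral in the early arm is optional and conditional, and standard care may send conventional patients home for outpatient work-up too. If the section 4 procedure counts refer to its 336 patients, at least 336 − 216 = 120 (36%) had neither endoscopy, though that series covers all GI bleeding. This also stands, and it is why the net imbalance is unknown.
- **The 27.8% is a weak guide.** Section 4 says capsules were often given after negative endoscopies, and the figure does not measure right-colon blood. It can only illustrate.
- **The telephone script is not in the file.** One cannot say that the calls ask nothing else, only that no capture of outpatient procedures is described.
- **Cost to the end of admission is a legitimate hospital-perspective outcome.** It is, if labelled so. It does not answer whether cost was avoided.

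A reader might infer that cost is a trial objective. Section 3 does not list it. It is a SAP secondary outcome.

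**Conclusion.** The point holds in a limited form. The collection window for procedures and the stated window for cost end at discharge. The early-capsule pathway can bring discharge forward and move endoscopy beyond it, and no capture of outpatient procedures is described. A lower procedure count or cost in that arm could therefore reflect postponement in part.

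The size cannot be estimated from the documents. The 8 to 22 hidden procedures per 80 patients assume one deferred endoscopy in 10% to 28% of early-arm patients, none in the conventional arm, and that each would otherwise have been done in hospital.

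Three stronger readings are tempting and not supported. The documents do not show that the procedure aim is met by relocating work, only that it could appear to be. They do not show a bias in endoscopic therapy, whose window is unstated. They do not show that the primary outcome is affected, whether time to diagnosis in the protocol or localization in the SAP. The procedure comparison also rests on the protocol alone, since the SAP does not list it. This is a worthwhile improvement to secondary outcomes and does not threaten the main result.

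**What to change.** Define one window for both arms that does not depend on discharge: randomization to day 30, inpatient plus outpatient, for invasive procedures, endoscopic therapy and GI-related direct cost. Use the record systems and finance source already named in Protocol section 10. Add one item to the existing 30-day call: any endoscopic or angiographic procedure done or scheduled since discharge, with its date. The call is timed from discharge with a margin of 3 days either way, so after a very short stay it can fall just before day 30; the record query closes that gap. Keep the in-admission count and cost as separately labelled outcomes. No change to clinical care is involved.

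The cost is a sentence in each document, one call item and a longer record and cost query. Some procedures at other hospitals will rest on patient report, and some will fall after day 30, which the scheduled item partly covers. Section 10 says that no additional PHI will be collected for the cost data, so a minor amendment may be needed. The extraction must come before the identifier keys are destroyed, which section 12 sets at completion of the primary analysis.

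If outpatient data can no longer be obtained, label these outcomes as in-admission only and do not conclude that procedures or costs were avoided.

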Once a subject is identified a page will be sent to a member of the research team (i.e. ED screener, research staff member, GI fellow on call, or GI attending on call) from the ED. In addition to this, the clinical research coordinator and or GI fellow will screen the Emergency Department triage software for patients who are listed as having NHGIB. Based on prior experience Ref Sachdev we expect for every 3 patients asked to participate in the study, there will be 1 patient who agrees to participate. In the emergency department study already cited, the Emergency Department at UMass sees about 350 patients annually for GI bleeding. Of these patients, approximately 230 patients have NHGIB. Given the 3:1 screening ratio, we would expect approximately 75 NHGIB patients every year to agree to participate in the study. In 24 months, we would expect to recruit up to 160 patients to our study.

INVESTIGATOR STUDY PLAN - REQUIRED

Once a subject is identified the subject will then be seen and examined by the GI fellow and attending as per standard of care and asked to participate in the study

Randomization

If inclusion/exclusion criteria are met, the consent discussion takes place and only if the subject agrees and consent is obtained, then the subject is randomized to the “Early Capsule Group” or “Conventional workup Group.” All patients in the “Early Capsule group” will receive the video capsule. Only some of the patients in the “Conventional Workup Group” will receive the capsule as indicated by what is considered the standard workup.

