We will assign patients to study ID numbers consecutively by the order of which they are enrolled in our study. For the Randomization Process we will be utilizing a random sorting generator to assign integers in a random order, corresponding to study IDs which allows researchers to randomly assign study participants into specific study groups. Assignments are put into a mail merge, locked with a password, and printed, then put into a sealed, security envelope, which is sealed with a Study ID sticker. The Randomization Scheme will allow us to attach particular Study ID numbers randomly to particular groups based on our criteria to have 80 subjects in the early capsule group and a comparable number in the conventional workup group. The envelope is only opened once all entry criteria have been met and the subject will be assigned a group. Subjects with a Study ID ending in 1-100 will be enrolled at University Campus. Subjects with a Study ID ending in 101-120 will be enrolled at Memorial Campus. Subjects with a Study ID ending in 121-160 will be enrolled at either campus, depending on enrollment. Enrollment will be competitive at the two locations and there is no specific quota to be reached at either location.

We plan to enroll up to 160 subjects in our study. 80 subjects will be randomized to the “early capsule” deployment group. This means that this group of subjects will have a VCE deployed as soon as possible after presentation to the ED, once the consent process has taken place, eligibility has been confirmed, and the subject has met the standard of care guidelines for preparation before capsule ingestion. Standard preparation for capsule ingestion means that a patient cannot eat for 10 hours prior to deployment of the capsule. Therefore, patients in our study will be asked when they had last eaten. If patients report that they have not eaten anything over the past 10 hours we will deploy the capsule immediately. If, however, patients say that they have eaten something over the past 10 hours we will take note of when they believe they last ate and will deploy the capsule 10 hours after the time that they last ate. In the pilot [Sachdev] study all patients in the early capsule arm received the capsule within a mean of 4 hours of admission to the ED, and none had food in the stomach on capsule examination.

INVESTIGATOR STUDY PLAN - REQUIRED

Procedure

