Throughout course of a study subject's participation in the study they will be followed for signs of adverse events to medication administration or for complications of capsule endoscopy. Adverse events will be documented as part of initial data analysis. This data analysis will be performed by the residents and fellows who are part of the study staff for this project.

Given that we anticipate minimal adverse events, any adverse events that occur will be reviewed by the study staff and the Primary Investigator within one week. This would include a complete analysis of the how the adverse event occurred in order to help prevent further events going forward. At that time the Primary Investigator will also assess cumulative reports.

14) Withdrawal of Subjects*

If the patient is unable to swallow the capsule we would remove them from the study.

Patients will be withdraw from study if the bleeding source is found to be outside of the stomach or intestines.

A subject can withdraw from the study at any time per their request.

15) Risks to Subjects*

This study is investigating the benefits of re-ordering the process of the current care algorithm for NHGIB. Video capsule endoscopy is already part of standard of care for many GI bleeding workups. This is not a new diagnostic modality and no new risk is being introduced from this technology itself. There are no anticipated risks to subjects who are randomized to the early deployment of the capsule and the diagnostic yield is expected to be at least comparable to the standard deployment.

One anticipated risk is a breach of confidentiality and to minimize this risk all identifiers will be destroyed. In order to minimize this risk, as described in question 12, identifiers will be destroyed. Data collected will be analyzed using study ID numbers only.

The most significant risk of VCE is capsule retention. This risk is the same for both groups and there is no anticipated unforeseen risk with early deployment. The risks do not change based on timing. Capsule retention is when the video capsule does not complete its transit throughout the GI tract. Studies have varied in their reports of the frequency of capsule retention with rates of about 1%, ranging from 1-13% of total cases. The

INVESTIGATOR STUDY PLAN - REQUIRED

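### Adverse-event follow-up names capsule and medication harms but no endoscopy complications, so a by-arm safety record would lean against early capsule

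*Protocol*

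**What the plan says.** **Scope of follow-up.** Section 13 of the protocol says that during participation "they will be followed for signs of adverse events to medication administration or for complications of capsule endoscopy". It adds that "any adverse events that occur will be reviewed by the study staff and the Primary Investigator within one week".

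**Who is exposed.** Section 10 (Randomization) says that all patients in the early arm "will receive the video capsule. Only some of the patients in the" conventional arm "will receive the capsule as indicated by what is considered the standard workup". The allocation is "80 subjects in the early capsule group and a comparable number in the conventional workup group".

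**Risk statement.** Section 15 says: "The most significant risk of VCE is capsule retention. This risk is the same for both groups". The next sentence but one, still in section 15, says that timing does not alter the risks. The same section states the hypothesis that early capsule may lead to fewer procedures.

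**What else is collected.** Section 10 (Review and Follow-Up) lists fluids, red-cell transfusion, procedure types and times, admission disposition including ICU, and discharge time. The calls at 3 and 30 days ask about recurrent bleeding and about hospital or emergency returns because of it. The SAP (Study outcomes) lists readmission, re-bleeding within 30 days and 30-day all-cause mortality. It lists no adverse-event comparison by arm and no procedure-complication outcome.

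**The concern.** The trial compares two work-up strategies, and part of the case for early capsule is that patients may be spared endoscopies. The harms of those endoscopies are therefore half of the safety question. Section 13 names the harms attached to the capsule, which one arm receives in full and the other in part. It does not name the harms of the procedures that the strategy hopes to reduce.

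If staff look for what section 13 names, capsule events will come almost entirely from the early arm, while a perforation or a sedation problem at colonoscopy has no designated place in the record. Two things are at stake. A table of adverse events by arm would make early capsule look worse than it is relative to conventional work-up. The trial also could not say whether fewer procedures led to fewer procedure complications.

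**Working it through.** **1. Where could a procedure complication be captured?**

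| Source | Names endoscopy, enteroscopy or angiography complications? | What it does cover |
|---|---|---|
| Protocol section 13 | No | Medication events, capsule complications, review of adverse events that occur |
| Section 10, hospital data | No | Procedure types and times, transfusion, fluids, disposition |
| Section 10, telephone calls | No | Recurrent bleeding and returns because of it |
| SAP, Study outcomes | No | Readmission, re-bleeding, mortality, among others |

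An emergency return for a procedure complication without bleeding falls outside the calls as described. The SAP's readmission outcome would count it only if the patient was readmitted and the trial learned of it, and then without a cause.

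**2. Capsule exposure by arm.** The early arm has 80 of 80. The documents give no conventional-arm rate, so three proxies are used, each an assumption:

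- Section 10 (Procedure): "estimated that 5-15% of patients will have small intestinal bleeding". This is a share with a bleeding site, not a share given a capsule. 80 × 0.05 = 4; 80 × 0.15 = 12.
- Section 4: "36 patients (10.7%) were given a video capsule during their stay". The figure reproduces: 36/336 = 10.7%. The cohort is all GI bleeding. 80 × 0.107 = 8.6.
- The same 36 capsules, supposing that all went to patients without hematemesis. Section 10 (Screening) puts these at about 230 of 350. 336 × 230/350 = 220.8; 36/220.8 = 16.3%; 80 × 0.163 = 13.0.

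**3. Expected retentions.** Expected cases = arm size × capsule share × retention per capsule. The chance of at least one = 1 − (1 − share × rate)^80. Section 15 gives about 1%.

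| Conventional capsule share | Capsules, early vs conventional | Exposure ratio | Expected retentions at 1% | Chance of at least one |
|---|---|---|---|---|
| 5% | 80 vs 4 | 20 | 0.80 vs 0.04 | 55% vs 4% |
| 10.7% | 80 vs 8.6 | 9.3 | 0.80 vs 0.09 | 55% vs 8% |
| 15% | 80 vs 12 | 6.7 | 0.80 vs 0.12 | 55% vs 11% |
| 16.3% | 80 vs 13.0 | 6.1 | 0.80 vs 0.13 | 55% vs 12% |

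The early arm supplies 80/93 = 86% to 80/84 = 95% of all capsule exposures. The absolute difference in expected retentions is 0.80 − 0.13 = 0.67 to 0.80 − 0.04 = 0.76. Per capsule given, the risk is 1% in both arms, a ratio of 1.0.

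Section 15 also quotes an upper figure of 13%, from a Crohn's disease study. Inflammatory bowel disease is excluded here, so 1% is the relevant value.

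**4. At the SAP's minimum size of 36 per group.** Capsules are 36 vs 1.8 to 5.9 (36 × 0.05; 36 × 0.163). Expected retentions at 1% are 0.36 vs 0.02 to 0.06. The ratios are unchanged.

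**5. What cannot be computed.** The documents give no complication rate for endoscopy, enteroscopy, angiography or sedation. The number of procedure complications at risk of going unrecorded is therefore unknown.

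**The case against.** The strongest reply is that no planned inference is distorted. Neither document sets an adverse-event endpoint or a between-arm test of adverse events. Section 13 describes monitoring of participants, and the endoscopies are standard care. That is correct. The point concerns what the trial will be able to report, not an error in a planned analysis.

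Four stronger readings are tempting, and the documents do not support them.

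- **A reader might infer that only capsule and drug events can ever be recorded.** Section 13 also provides for review of any adverse event that occurs, and its wording on medication is not limited to prokinetics, so it could take in sedatives. But a provision for review does not say what is looked for, and procedure complications are still not named.
- **A reader might infer that harm from waiting for the capsule goes unseen.** Transfusion, disposition, re-bleeding, readmission and death are collected in both arms and would show much of it. A fasted patient also receives the capsule at once.
- **A reader might infer that section 15 is false in calling the retention risk equal.** The sentence concerns the risk of the capsule examination, and the text goes on to timing, so a per-capsule reading is natural and consistent. Against that, the protocol uses the word groups for the randomised arms, and section 15 also speaks of risks to those randomised to early deployment. The wording is ambiguous, not refuted.
- **A reader might infer a large prokinetic imbalance.** At 1 in 8, about 80/8 = 10 early-arm patients would receive one. No conventional-arm rate is given, and the protocol says these drugs are commonly used before upper endoscopy, so no contrast can be drawn.

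**Conclusion.** The concern holds in limited form. The named targets of adverse-event follow-up are tied largely to one arm's exposure, and no part of either document names complications of the procedures that early capsule is meant to reduce. An adverse-event table built from this record would lean against early capsule and could not test whether fewer procedures means fewer procedure harms.

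The exposure gap is large (about 6- to 20-fold), but its consequence for retention is small: less than one expected case at 1%. The fold range rests on proxies for conventional-arm capsule use. The direction holds for any conventional-arm share below 100%. This is a worthwhile and inexpensive improvement to the safety record, and it does not threaten the primary comparison.

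**What to change.** - **Section 13:** state that adverse events are recorded identically in both arms from randomisation to the 30-day contact. Include complications of any diagnostic or therapeutic GI procedure and its sedation, unplanned ICU transfer, and capsule and medication events.
- **Telephone script:** ask about any return to hospital or emergency care, with the reason, so that procedure complications without bleeding are captured.
- **SAP:** add a descriptive table of these events by randomised arm. No formal test is needed.
- **Section 15:** say that retention risk is the same per capsule given, but that assignment to the early arm raises the chance of receiving a capsule to 100%, against a minority expected in the conventional arm.

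The cost is a few more fields in a chart review that already covers procedures and disposition, more events to log, and a slightly less favourable risk statement. No treatment or work-up rule changes.
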